5.2 Exclusion Criteria

- Individuals with poor conversant English
- Patients with cognitive impairment
- Patients without suitable digital devices or inability to access the internet

5.3 Assignment and Randomisation Number

The data regarding VA assessment of the left eye only of individuals will be analysed.

5.4 Method of Blinding

The health care assistant or orthoptist undertaking the standard chart-based test will not have knowledge of the DigiVis VA results.

5.5 Emergency Unblinding

Not applicable

5.6 Subject withdrawal criteria

The individual will be withdrawn from the study if it he/she is unable to access the DigiVis website or undertake the test twice.

6 Study procedure and assessments

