2.3 Safety data

The software is CE marked Class1 medical devices and is delivered on a web-site accessed from the patients' own digital devices, no safety issues are foreseen.

3 Rationale for Study

Validation of the accuracy of the software package will enable recommendation of its use in conjunction with telephone consultation to inform clinical decision making during and after the lockdown period as social distancing increases the need for virtual consultations.

4 Trial objective and purpose

Primary objective: to compare VA assessment of self-testing on the DigiVis website to formal VA measurement using chart-based tests in clinic.

Secondary objective: to assess the repeatability and usability of the software.

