4.3 Study objectives

4.3.1 Primary research question

Is the visual acuity score measured by home self-testing with DigiVis comparable to current chart-based clinic methods?

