6.1 Informed consent

Subjects who fulfil the inclusion criteria will undergo the following consent process:

First telephone call:

The researcher will telephone patients prior to their scheduled face to face clinic appointment for an introductory phone call to explain the study and to determine if any exclusion criteria apply.

If interested in the study at this first contact, the individual will be directed to the website and shown how to access the study information and consent form. The researcher will go over both forms with the potential participant. A convenient time for a follow up call at least 30 minutes after the first will be arranged to allow the patients

to consider participation and discuss with friends and family. They will be informed that non-participation will not affect patient care. Access to the website is possible via a password and no personal information is stored in the web-server.

Second telephone call:

If the patient wishes to participate in the study they will be asked to read and electronically consent to undertaking the DigiVis test on the website itself. The researcher will then help them undertake the first VA test and will note down the VA values. The participant will be asked to undertake the test themselves a second time before their scheduled clinic appointment and note down, or take a photo of, their VA score.

Clinic assessment:

At this appointment, as standard practice, chart-based VA will be assessed by a health care professional (who is masked to the result of the DigiVis scores). A researcher will approach the subject during their visits and the formal study consent form will be signed and the usability feed-back documented.

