9.4 Procedure to account for missing or spurious data

The first DigiVis score will be taken down over the telephone at the time of the second call. It is possible that the participant may forget to take the DigiVis a second time or forget to bring the VA score. Where this occurs, the DigiVis test will be repeated in clinic.

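### Section 5.6 withdraws from the whole study anyone unable to do DigiVis twice, so the primary agreement analysis may select on performance of the test being validated

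*Combined protocol and SAP*

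**What the plan says.** All references are to the combined protocol and SAP.

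- **Withdrawal (5.6).** "The individual will be withdrawn from the study if it he/she is unable to access the DigiVis website or undertake the test twice". The withdrawal is from the study, not from one analysis.
- **Primary question (4.3.1).** "Is the visual acuity score measured by home self-testing with DigiVis comparable to current chart-based clinic methods". The primary objective in section 4 is likewise "to compare VA assessment of self-testing on the DigiVis website to formal VA measurement using chart-based tests in clinic". Neither states that two DigiVis scores are needed. Repeatability is a secondary question (4.3.2).
- **First DigiVis test (6.1).** "The researcher will then help them undertake the first VA test and will note down the VA values". Section 9.4 confirms the timing: "The first DigiVis score will be taken down over the telephone at the time of the second call".
- **Second DigiVis test (6.1).** "The participant will be asked to undertake the test themselves a second time before their scheduled clinic appointment".
- **Chart test (6.1).** This is done at the clinic visit as part of routine care.
- **Missing second score (9.4).** "It is possible that the participant may forget to take the DigiVis a second time or forget to bring the VA score". The remedy is: "Where this occurs, the DigiVis test will be repeated in clinic".
- **Analysis (7 and 9.1).** Bland-Altman methods and test-retest variability are named. No analysis set is defined. The plan does not say which DigiVis score is set against the chart, or what happens to data recorded before a withdrawal.

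**The concern.** A requirement that only a secondary question necessarily imposes has become a condition for staying in the whole study. Consider a participant who completes the first test by telephone and then cannot do the second. One DigiVis score is on record, and a chart value will be obtained in clinic at no extra cost. Under 5.6 this person is withdrawn, and nothing says the pair is kept.

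The selection is on performance of the device under validation. People who cannot repeat the test are plausibly those whose first score is noisiest. If they leave the primary analysis, the SD of the differences is estimated in easier participants, and the limits of agreement favour DigiVis. This matters because section 3 intends the result to support recommending the app alongside telephone consultations. Recruiting replacements to reach 250 would restore the number but not remove the selection.

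**Working it through.** **Who is affected**

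| Situation | Section | First score on record? | Result |
|---|---|---|---|
| Cannot access the website | 5.6 | No | Withdrawn; no pair to lose |
| Forgot second test, or did not bring the score | 9.4 | Yes | Test repeated in clinic; stays in |
| Did the first test, cannot do a second | 5.6 | Yes | Withdrawn; no text keeps the pair |

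Only the third row is at issue. Sections 5.6 and 9.4 do not refer to each other.

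**The plan's own figure.** 100 adults + 150 children = 250, which agrees with 4.3.3. The power calculation behind 250 cannot be reproduced, because the mean and SD of the differences, the maximum allowed difference, alpha and power are not given. The point does not depend on it.

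**Size of the selection effect.** The inputs are assumptions, as the documents give none:
- *p*, the share with a first score and a chart value who cannot do a second test: 5%, 10% or 20%.
- *k*, the SD of their DigiVis-chart differences divided by the completers' SD: 1.5 to 3.
- Equal mean difference in the two groups.

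The formulas are:
- R = all-pairs SD / completer SD = √[(1 − p) + p·k²].
- Limits are mean ± 1.96·SD, so completer-only limits are narrower by 1 − 1/R.

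Example with p = 0.10 and k = 2: R = √(0.90 + 0.10 × 4) = √1.30 = 1.140, and 1 − 1/1.140 = 12.3%.

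| p | k = 1.5 | k = 2 | k = 3 |
|---|---|---|---|
| 5% | √1.0625 = 1.031; 3% | √1.15 = 1.072; 7% | √1.40 = 1.183; 15% |
| 10% | √1.125 = 1.061; 6% | √1.30 = 1.140; 12% | √1.80 = 1.342; 25% |
| 20% | √1.25 = 1.118; 11% | √1.60 = 1.265; 21% | √2.60 = 1.612; 38% |

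If k = 1, R = 1 and there is no narrowing. If the mean differences are unequal, the all-pairs variance gains a further positive term, so the all-pairs limits widen more.

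**Precision.** The half-width of the 95% CI for one limit is 1.96·SD·√[1/n + 1.96²/(2(n − 1))]. At a common SD this is 0.212 SD for n = 250, 0.224 SD for n = 225 and 0.237 SD for n = 200. The SD is not common under the assumptions above. In completer-SD units, all 250 pairs give approximately:
- p = 0.10, k = 2: 0.212 × 1.140 = 0.242, against 0.224 in 225 completers.
- p = 0.20, k = 1.5: 0.212 × 1.118 = 0.237, against 0.237 in 200 completers.

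Keeping these participants therefore gives no gain in precision in these cases. The issue is selection.

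**The case against.** Five objections deserve an answer.

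1. *A reader might infer that agreement would be estimated only in people who manage the app unaided.* The documents contradict this. The first test is done with the researcher's help (6.1), and a forgotten or unreported second test is repeated in clinic (9.4). Someone with no unaided home result can stay in. Section 5.6 requires two tests, not unaided ones.
2. *A reader might infer that the plan orders the recorded pair to be discarded.* It does not say so. Exclusion is the natural reading of withdrawal from the study, but the text is silent on data already collected. For someone withdrawn before the clinic visit, the chart half of the pair does not yet exist, and formal written consent is signed only at that visit (6.1, 11.1). This stands, and it is why retention must be subject to consent.
3. *The primary analysis might use the second score or a mean of the two.* The synopsis lists two DigiVis self-tests among the comparators, and the plan does not name the score used. The two-test rule could then serve the primary analysis. This stands as far as it goes: the comparison can be made with one score, but the plan has not said that it will be. It also means the assisted first score should not be made primary by default, since 4.3.1 asks about home self-testing.
4. *A loss of precision might be claimed.* It fails, as shown in the working. A fall below 250 is not established either, because 9.5 allows further recruitment.
5. *True inability at the second test may be rare.* Forgetting is covered, the first test was assisted, and people without devices or internet are excluded at entry (5.2). This is fair. The upper end of the range has no support in the documents.

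None of this supplies text that keeps the first score of a participant unable to repeat the test.

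**Conclusion.** The point holds in a limited form. Section 5.6 applies a two-test condition to the whole study, 9.4 does not cover true inability, and no provision keeps a score already recorded. On the natural reading, the primary Bland-Altman analysis would leave out participants because of how they performed on the test being validated, and its limits could be too narrow.

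The direction rests on the assumption that those unable to repeat have noisier differences. The size is unknown and the range in the working is purely illustrative: from 3% (5% lost, k = 1.5) to 38% (20% lost, k = 3), and nil if their differences are no noisier and have the same mean. The change is worth making because the rule is explicit and the correction is cheap.

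**What to change.** - **5.6:** state that inability to do a second test ends only the repeatability part. Reconcile this with 9.4, so that forgetting and inability each have a stated route.
- **9.1:** state that the primary analysis includes every left eye with at least one valid DigiVis score and a clinic chart score, subject to consent. Name in advance which DigiVis score is used when two exist.
- **Test-retest:** restrict it to participants with two DigiVis scores.
- **Reporting:** give both denominators, and the number unable to access the website or repeat the test, with reasons.
- **Sensitivity analyses:** repeat the primary analysis in those with two scores, and by how the test was done (assisted, unaided at home, or in clinic).

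The cost is a few sentences, a record of how each test was done, and confirmation that the consent wording covers keeping the data. No extra patients or tests are needed. The downside is that the limits of agreement may come out wider, and some retained pairs will rest on the assisted first test alone. The analysis by type of test makes that visible.

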4.3.2 Secondary research question

What is the test-retest variation (repeatability) of the DigiVis system?

What is the ease of use of the app and what features could be modified to improve usability? Study endpoints

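### Section 5.6 withdraws consented participants who cannot do DigiVis twice, so usability would be reported mainly for people who could complete the test

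*Combined protocol and SAP*

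**What the plan says.** - **Withdrawal.** Section 5.6 removes a person who is "unable to access the DigiVis website or undertake the test twice".
- **Objective.** Section 4 states: "Secondary objective: to assess the repeatability and usability of the software". Section 4.3.2 asks: "What is the ease of use of the app and what features could be modified to improve usability". Section 9.1 plans a quantitative analysis of preference and usability, with no population or denominator named.
- **The two home tests.** Section 6.1 treats them differently. For the first, "The researcher will then help them undertake the first VA test and will note down the VA values". For the second, "The participant will be asked to undertake the test themselves a second time before their scheduled clinic appointment".
- **When usability is collected.** In section 6.1 this happens at the clinic visit, where "the formal study consent form will be signed and the usability feed-back documented".
- **Data items.** Section 6.2 lists two DigiVis scores, a chart score, a usability score and patient comments. Completion, failed attempts and reasons for withdrawal are not listed.
- **Missing second test.** Section 9.4 repeats DigiVis in clinic when the participant forgets the test or does not bring the score.
- **Access before entry.** Section 5.2 excludes "Patients without suitable digital devices or inability to access the internet". At the first call in section 6.1 the person is directed to the website and "shown how to access the study information and consent form". Electronic consent is then given on the website.

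**The concern.** DigiVis is meant for unaided use at home. The second test is the only planned home measurement that participants are asked to do by themselves. Someone who managed the helped test but cannot do the unaided one is among the most informative participants for the section 4.3.2 question, including the part about which features to change. Section 5.6 removes that person before the visit at which usability is documented.

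A usability or preference figure from the people who remain answers a narrower question: how the app is rated by those who could complete it. Sections 2.1, 3 and 14 look ahead to recommending the app for clinical use. For that purpose a reader also needs to know what share of those who agreed to try could complete it. If the reason for a failure is not recorded at the time, it may not be recoverable later.

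**Working it through.** The plan states no figure on this point, so there is none to reproduce. The check has two parts.

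**1. Following consented participants through the plan**

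| Participant, after electronic consent | What the plan provides |
|---|---|
| Completes both tests | Scores, usability score and comments at the clinic visit |
| Forgets the second test or the score | DigiVis repeated in clinic (9.4) and kept |
| Completes the helped test, cannot do the second | Withdrawn (5.6); no reason field; no provision for feedback |
| Cannot complete even the helped test | Withdrawn (5.6); no reason field; no provision for feedback |

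The last two rows carry the strongest evidence of poor usability, and they are the rows removed. Without a reason field, forgetting and inability cannot be told apart afterwards.

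**2. What could be at stake (illustration only)**

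Inputs:
- f, the share of consented participants unable to complete: assumed 5, 10 or 20%. The documents give none.
- Share favourable among completers: assumed 80%. Section 2.1 gives this figure for children's preference in early testing; it is not an ease-of-use result.
- p, the share favourable among those unable to complete: assumed 0, 40, 80 or 100%.

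Share favourable among all who tried = 0.80(1 − f) + p·f. For example, f = 0.10 and p = 0 gives 0.80 × 0.90 = 72%.

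| f | p = 0 | p = 0.40 | p = 0.80 | p = 1 |
|---|---|---|---|---|
| 5% | 76% | 78% | 80% | 81% |
| 10% | 72% | 76% | 80% | 82% |
| 20% | 64% | 72% | 80% | 84% |

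The completers-only figure is 80% throughout, so its bias is f(0.80 − p). The range runs from 16 points too high (80 − 64) to 4 points too low (80 − 84).

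For scale, the Wilson 95% interval is [p̂ + z²/2n ± z√(p̂(1 − p̂)/n + z²/4n²)] / (1 + z²/n), with z = 1.96. For 200 of 250 it is 74.6 to 84.5%, a half-width of 4.94 points. The bias exceeds that half-width once f passes 4.94/0.80, about 6%, if no failure is favourable, or 4.94/0.40, about 12%, if failures are half as favourable. If failures match completers it never does. Comparing bias with a half-width is a yardstick chosen for this review, not one set by the plan.

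**3. Would a completion rate be informative at the planned size?**

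Wilson 95% intervals, with assumed counts and the section 9.2 group sizes:

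| Unable to complete | Share | 95% CI |
|---|---|---|
| 25 of 250 | 10% | 6.9 to 14.3% |
| 10 of 100 adults | 10% | 5.5 to 17.4% |
| 15 of 150 children | 10% | 6.2 to 15.8% |
| 0 of 250 | 0% | 0 to 1.5% |

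The planned sample would give a usable completion rate overall and a rougher one by age group, even if failure is rare.

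**The case against.** **The access limb is nearly empty.** Section 5.2 removes people without devices or internet, the first call shows people the website forms, and consent is given on the site. Someone who cannot reach it normally never becomes a participant. This stands. A reader might infer from section 5.6 that the study loses many participants through failed access; the documents do not support that, and the point rests on the test-twice limb.

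**The remaining group may be small.** Staff may offer the clinic repeat to anyone who arrives without a second score, whatever the cause. That is possible, but section 9.4 is written for forgetting, and a repeat in clinic is not an unaided home test.

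**Completion may be captured implicitly.** The section 6.2 list is not worded as exhaustive, and a blank second score would mark non-completion wherever the record is kept. Section 5.6 does not say that data are deleted, that withdrawals go uncounted or that feedback may not be sought. All of this is correct. A reader might infer that failures will be erased, and the text does not say so. What remains is that the rule withdraws these people and the plan provides neither a reason item nor feedback from them. Patient comments come from those seen at the clinic visit and are not a count.

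**The illustration shows nothing about this trial.** Every share in it is assumed, it applies a children's preference figure to a mixed sample, and the form of the usability score is not specified. This stands. The figures show only that the bias could matter or could be nil.

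**Usability is secondary and has no stated threshold.** This stands too, and it limits the weight of the point.

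**Conclusion.** The point holds for people who consented electronically and cannot complete the test twice. Followed as written, the plan selects usability and preference data towards people who could complete it. This conclusion rests on the text of sections 4, 4.3.2, 5.6, 6.1, 6.2, 9.1 and 9.4, and not on the illustrative figures.

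The size cannot be found from the documents. The direction is not strictly established either: an overstatement is plausible, but it requires that those unable to complete rate the app less favourably than completers do.

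A reader might also infer that the primary comparison is biased. The documents do not support that. Any effect there is probably small, and it is zero if a person with one valid home score and a chart score is kept in. The plan does not say whether such pairs are kept; that is a separate and minor point.

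The change is worth making because it is cheap and alters what can be concluded on a secondary objective.

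**What to change.** 1. Amend section 5.6 so that, after electronic consent, inability to complete either test is recorded as an outcome with its reason and is not a ground for withdrawal. The record should separate unable from forgot, and the helped first test from the unaided second.
2. Seek usability feedback and written consent from these people at the clinic visit they already attend. Written consent matters because until that visit they have given only electronic consent (sections 6.1 and 11.1).
3. Report the completion rate among all who consented electronically, for adults and children, beside the usability and preference results. Do not code failures as unfavourable; their ratings should be reported as given.
4. Give failures to reach the website before consent only as an anonymous count.

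The cost is one data field, a change of wording and slightly more feedback work at a visit where consent and feedback are already planned. The sponsor should accept that the usability result may look less favourable.

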6.1 Informed consent

Subjects who fulfil the inclusion criteria will undergo the following consent process:

First telephone call:

The researcher will telephone patients prior to their scheduled face to face clinic appointment for an introductory phone call to explain the study and to determine if any exclusion criteria apply.

If interested in the study at this first contact, the individual will be directed to the website and shown how to access the study information and consent form. The researcher will go over both forms with the potential participant. A convenient time for a follow up call at least 30 minutes after the first will be arranged to allow the patients

to consider participation and discuss with friends and family. They will be informed that non-participation will not affect patient care. Access to the website is possible via a password and no personal information is stored in the web-server.

Second telephone call:

If the patient wishes to participate in the study they will be asked to read and electronically consent to undertaking the DigiVis test on the website itself. The researcher will then help them undertake the first VA test and will note down the VA values. The participant will be asked to undertake the test themselves a second time before their scheduled clinic appointment and note down, or take a photo of, their VA score.

Clinic assessment:

At this appointment, as standard practice, chart-based VA will be assessed by a health care professional (who is masked to the result of the DigiVis scores). A researcher will approach the subject during their visits and the formal study consent form will be signed and the usability feed-back documented.

6.2 Personal data

The personal data recorded for the study will be hospital number and date of birth. Study data will include: DigiVis VA score x 2, chart based VA score, usability score and patient comments.

7 Evaluation of Results

Bland Altman statistical methods and calculation of test-retest variability will be calculated after 100 adults and 150 children have been tested.

8 Assessment of Safety

No safety issues are expected during this study because the patients are using their own devices and the clinic element of the study is standard clinical practice.

9 Statistics

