DigiVis: validation of self-testing visual acuity web-based app to aid ophthalmic telephone consultations during Covid19 lockdown and subsequent social distancing crisis.

Clinical Study Protocol

Protocol Number: DigiVis v0.1

NCT: **IRAS ID 196573**

Document date: **15th July 2020**

Study Title: DigiVis: validation of self-testing visual acuity web-based app to aid ophthalmic telephone consultations during Covid19 lockdown and subsequent social distancing crisis.

Investigational Product: Web-based Visual Acuity software

Protocol Version: Version 0.1

Chief investigator: Miss [name] MBBS MD MA FRCOphth
Consultant Paediatric Ophthalmologist, Addenbrooke's Hospital

Investigator's address: [name], Ophthalmology Department
[name]
Cambridge
[name]

Study Location: Addenbrooke's Hospital, Cambridge (CUHFT)

[contact]

Study Sponsor: Cambridge University Hospitals NHS Foundation Trust

1 Study Synopsis

Title of clinical trial	DigiVis: self-testing vision app for telephone consultations
Sponsor name	Cambridge University Hospitals NHS Trust
Medical condition under investigation	Visual Acuity (VA) assessment
Purpose of clinical trial	To validate VA self-assessment using DigiVis software by comparison to current chart-based tests
Primary objective	Comparison of VA assessment with DigiVis software to clinic-based VA assessment.
Secondary objective (s)	Calculation of test-retest variability. Assessment of usability and preference.
Study Design	Prospective quantifiable comparison study
Study Endpoints	Completed testing on a sufficient number of individuals to give good statistical power.
Sample Size	Approximately 250 patients in total
Summary of eligibility criteria	Patients aged between 5 and 85 due to attend scheduled clinic appointment with vision $+0.8\log\text{MAR}$ (6/38) or better in their left eye. Patients with access to two appropriate digital devices. Ability to understand English and log on to the website.
Active comparator product(s)	Clinic VA charts: LogMAR visual acuity chart, SLT childrens' vision chart.
Route(s) of administration	Visual test
Maximum duration of treatment	2 clinical interventions of 5 minutes each at home
Procedures: Screening & enrolment	Eligible patients will be identified from electronic patient record prior to a scheduled clinical appointment. Telephone enrolment will be undertaken.
Comparators	VA test at the scheduled clinic appointment. Two DigiVis self-test VA measurements. Patient preference.

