4.3.3 Primary endpoint

Clinical testing will cease once at least 250 individuals have been recruited to enable adequate statistical power using Bland-Altman calculations.

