9.1 Statistical methods to be employed

Bland-Altman statistics similar to those illustrated in the initial validation studies will be used. In addition test-retest variability and quantitative comparison of preference and usability will be analysed. Sample size requirements have been calculated using MedCalc based on the results from the initial validation studies (graph 1&2)

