9.2 Number of Subjects to be enrolled

100 adults

150 children aged 5-16years

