9.5 Definition of the end of the trial

Interim data analysis will be undertaken once 100 adults and 150 children have been tested to ensure sufficient statistical power. If insufficient further recruitment may be necessary.

10 Direct access to source data / documents

The investigators will permit trial related monitoring, audits, REC review, regulatory inspections.

11 Ethical considerations – none foreseen

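### Does the plan need a stated Bland-Altman analysis by age group and chart, given separate adult and child targets and two comparator charts?

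*Combined protocol and SAP*

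**What the plan says.** - Section 9.2 sets two recruitment targets, 100 adults and "150 children aged 5-16years". Section 4.3.3 attaches power to the total: testing stops once "at least 250 individuals have been recruited to enable adequate statistical power using Bland-Altman calculations".
- Section 7 uses the two counts as the point at which analysis starts: "Bland Altman statistical methods and calculation of test-retest variability will be calculated after 100 adults and 150 children have been tested". Section 9.5 repeats them for the power check: "Interim data analysis will be undertaken once 100 adults and 150 children have been tested to ensure sufficient statistical power".
- Section 9.1 gives the method by reference: "Bland-Altman statistics similar to those illustrated in the initial validation studies will be used". It bases the sample size on the same earlier studies and points to graphs 1 and 2, which are not in the supplied text.
- The synopsis lists the comparators, beginning "Clinic VA charts: LogMAR visual acuity chart, SLT"; the SLT is described there as a children's chart. Section 6.1 says only that "as standard practice, chart-based VA will be assessed by a health care professional". No rule states who is tested on which chart.
- Section 6.2 records hospital number and date of birth, and adds: "Study data will include: DigiVis VA score x 2, chart based VA score, usability score and patient comments". Chart type is not named.
- Section 5.3 restricts analysis to the left eye, so each person contributes one pair of readings.

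**The concern.** Limits of agreement will be read as the likely error of a single home reading, and section 3 intends the app to inform decisions in telephone consultations. Children may be less consistent than adults on either test, and a children's chart may differ systematically from a LogMAR chart. A single pooled set of limits could then be too wide for one group and too narrow for the other, or be centred on a bias that fits neither. Recruiting to group targets without saying that the groups will be reported looks like an oversight, and it leaves the choice to pool or split open until the data are seen. If the chart were not recorded, bias by chart could not be reported at all.

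**Working it through.** **The plan's own figure.** 100 + 150 = 250, which agrees with section 4.3.3. The MedCalc sample-size calculation cannot be reproduced, because the visible text gives no expected bias, SD of differences, allowed difference, alpha or power.

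**Precision by group.** With s the SD of differences, the 95% confidence half-width of one limit is t × s × √(1/n + 1.96²/(2(n − 1))).

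- n = 100: 1.984 × √(0.01 + 3.8416/198) = 0.340 s
- n = 150: 1.976 × √(0.00667 + 3.8416/298) = 0.276 s
- n = 250: 1.970 × √(0.004 + 3.8416/498) = 0.213 s

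At an assumed s of 0.10 logMAR these are 0.034, 0.028 and 0.021. Group limits are less precise than pooled ones, but they can be estimated without extra patients.

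**What pooling would do, if it were the only analysis.** The weights are 100/250 = 0.4 and 150/250 = 0.6. With group SDs sa and sc, adult bias 0 and child bias d:

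- pooled bias = 0.6d
- pooled SD = √(0.4sa² + 0.6sc² + 0.24d²)
- limits = pooled bias ± 1.96 × pooled SD
- coverage from the normal distribution

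For example, sa = 0.10, sc = 0.15, d = 0 gives √(0.004 + 0.0135) = 0.1323 and limits of ±0.259. All SDs and biases below are assumptions, in logMAR. The shift is the largest gap between a pooled limit and the group's own limit. The half-width of that own limit is in brackets.

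| sa, sc, d | Pooled limits | Coverage, adults / children | Shift, adults | Shift, children |
|---|---|---|---|---|
| 0.10, 0.15, 0 | ±0.259 | 99.0% / 91.6% | 0.063 (0.034) | 0.035 (0.041) |
| 0.15, 0.10, 0 | ±0.240 | 89.0% / 98.4% | 0.054 (0.051) | 0.044 (0.028) |
| 0.10, 0.12, 0 | ±0.220 | 97.2% / 93.4% | 0.024 (0.034) | 0.015 (0.033) |
| 0.12, 0.12, 0.05 | −0.210 to 0.270 | 94.8% / 95.2% | 0.035 (0.041) | 0.025 (0.033) |
| 0.08, 0.15, 0 | ±0.248 | 99.8% / 90.2% | 0.092 (0.027) | 0.046 (0.041) |
| 0.10, 0.10, 0.10 | −0.158 to 0.278 | 94.1% / 95.8% | 0.082 (0.034) | 0.062 (0.028) |

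With equal SDs and equal bias there is no distortion. Modest differences (rows 3 and 4) stay within sampling error, although in row 4 the adult misses become lopsided: 4.0% below and 1.2% above. Larger differences do not stay within it.

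**Where pooling starts to matter.** Take equal biases, children more variable, and r = sc/sa.

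- Adults: 1.96 × (√(0.4 + 0.6r²) − 1) = 0.340 gives r ≈ 1.28.
- Children: 1.96 × (r − √(0.4 + 0.6r²)) = 0.276r gives r ≈ 1.70.

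The documents give no SD or bias by group, so they do not show whether either ratio is reached.

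**Can the planned data supply the split?**

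- *Age:* yes. Date of birth is recorded, and section 9.2 defines children as 5–16.
- *Chart:* probably. The list in section 6.2 is worded as what the data will include, not as a closed set. The chart test is routine clinic work, and the hospital number allows linkage to the clinic record. Section 12 keeps identifiable data for 6–12 months after the study. The documents do not confirm that the clinic record names the chart.
- *Chart apart from age:* only where both charts are used within one age group. The number tested on each chart is not given.

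**The case for a change.** The strongest case for a change is that agreement with the chart is the primary objective, the reported limits will describe individual patients, and no visible sentence promises results by group. An earlier illustration that the new analysis will merely resemble is a weak commitment. Without a written rule, the choice to pool or split could follow the data. If the 250 was justified as a total, its adequacy does not carry over to each group: the half-widths rise from 0.21 SD to 0.34 and 0.28 SD. Asking for group results would cost a few tables and one data field.

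Most of this is accurate as description. The sentence is absent from the visible text, chart type is not listed, and precision is lower by group. What does not stand is the step from there to a defect. The two missing graphs may show the split, and figures lost from the supplied text cannot be counted against the plan. Sections 7 and 9.5 both name the two groups where analysis and the power check are triggered, which fits reporting each group and does not fit a pooled-only rule any better. The primary question in section 4.3.1 asks about agreement with current clinic methods in general, and a pooled estimate against usual practice is a legitimate answer to it. The plan proposes no test to justify pooling, so there is no such test to guard against.

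**Conclusion.** The concern does not call for a change. It identifies a reporting choice that the visible text leaves unwritten, not an instruction that would produce a wrong result. An analyst holding this dataset would naturally show adults and children separately beside the pooled limits; date of birth is on file and the sample size is unaffected. Chart type is the less certain part. It is likely to be recoverable through the hospital number, but this rests on the clinic record naming the chart.

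The possible harm depends on two things the documents do not establish: that only pooled limits would be reported, and that the groups differ appreciably. Under the assumed values above, the effect runs from nothing to coverage of about 89% in the worse-served group, with limits displaced by up to about 0.09 logMAR. A sentence saying that results will be given by age group, and a note that the chart is captured, would be harmless optional clarifications. Nothing in the design, sample size or primary analysis depends on them.
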